###### Safety (Treatment Emergent Adverse Event):

- Adverse events that started after 28 days will be considered as Post Treatment Adverse Events (PTAE)

###### All other procedures:

Only observed cases within 3 days after study treatment last intake will be used:

- Missing data will remain missing
- Will also be considered as missing any data collected more than 3 days after study treatment last intake

###### Note:

- Data collected at Visit 3 being an early treatment discontinuation, should not be taken into account for Week 24 (i.e. actual V3) data descriptions
- For OCUT analysis where data available at Week 28 (i.e. V4) should be described, all Week 28 (i.e. V4) data that are within 4 weeks  $\pm$  2 weeks compared with Week 24 (i.e. V3) are to be taken into account.  
Data collected at Visit 4 being the visit following an early treatment discontinuation, should not be taken into account for Week 28 (i.e. actual V4) data descriptions
- For all analysis based on biopsy data, data collected at actual V3 should be taken into account as well as data collected at Visit 3 being an early treatment discontinuation.

#### 4.1.7 Handling centres

In order to explore any potential “center” or geographical effect on primary criteria, centers need to be pooled in order to have enough patients by “group”.

Three strategies of center pooling will be used to explore any potential “center” effect:

1. Centers will be distributed in 2 groups: Bulgaria (the main recruiter in the study) and all other countries
2. Centers will be distributed in 3 groups according to the number of randomised and treated patients (i.e. in the FAS, see section 4.3.3):
  - 3 or less patients randomised and treated
  - From 4 to 9 patients randomised and treated
  - 10 or more patients randomised and treated

#### 4.1.8 Visit reallocation

Not Applicable.

## 4.2 Sample size calculation

The expected rate of responders according to the retained definition was estimated to 10% for the placebo by a group of clinical experts. An excess rate of responders of 20% was accepted as clinically pertinent. It corresponds to a multiplication of chance of success (responders) of 3 and a NNT (Number Needed to Treat) of 5. The sample size required to reach a power of at least 80% is 72 patients per group with a two-sided alpha of 0.025 (adjustment for multiplicity). The sample size is sensitive to the rate of responders in the placebo group. For example, if the rate of responders is 15% instead of 10% then 85 patients are required. If the true rate is lower than 10% then less patients may be sufficient. The sample size is therefore rounded in the conservative side of 75 patients per group.

Based on the experience of previous clinical trials, it is estimated that 100 patients per group will need to be screened to randomise 75 patients after central reading of liver biopsy confirms the NASH diagnosis and activity (screening failure rate of 25%). However, as detailed in section 3.5, the observed screening failure rate was of 72%), consistent with all other clinical trial performed in NASH with such a high screening failure rate.

In case the end of study liver biopsy slides are not available or not interpretable in more than 5% of patients, an amendment will be submitted to increase sample size accordingly.

### 4.3 Analysis populations

#### 4.3.1 Screened patients

The screened patients will consist of all patients who signed the informed consent (with an informed consent date completed).

#### 4.3.2 Randomized set of patients

The randomized set of patients will consist of all randomized patients.

In case of treatment error, the treatment assigned in the randomization list will prevail over the actual received treatment. Additionally, in case of stratification error at randomization, strata assigned via the randomization will be taken into account for the analysis.

*Reminder: Randomisation stratified on diabetes (presence/absence).*

#### 4.3.3 Full analysis set (FAS)

The full analysis set will consist of all randomized patients who received at least one dose of the assigned treatment.

In case of error in the assignment of treatment, the actual treatment will be used in the FAS instead of the treatment assigned in the randomization list.

Additionally, in case of stratification error at randomization, actual strata will be taken into account for the analysis.

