### **9.5 Data sets Analyzed**

#### **- Full analysis set (FAS)**

The full analysis set consists of all randomized patients who received at least one dose of the assigned treatment. In case of error in the assignment of treatment, the actual treatment will be used in the FAS instead of the treatment assigned in the randomization list.

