#### 9.7.4 *Efficacy Analyses*

##### Primary efficacy analysis

The primary population will be the intent to treat FAS population composed of all randomized subject who received at least one dose.

The primary efficacy endpoint will be a binary variable (responder / non responder) based on the change from baseline to Week 24 of the SAF activity score. Responder is defined as a decrease from baseline to week 24 of at least 2 points of the SAF activity score combining hepatocellular inflammatory and ballooning without worsening of fibrosis.

The primary tests of hypotheses will be the Cochran Mantel Haenszel test stratified on diabetes comparing the high dose to placebo and the low dose to placebo. The ascending Hochberg procedure will be used for adjusting the type one error which is globally set at 0.05 two-sided. The primary measure of the effect size will be the CMH odds ratio with an adjustment for diabetes. Because the odds ratio is not easy to interpret when the rate of responders in the placebo group is not very small the odds ratio (OR) and its confidence interval will be converted in Risk Ratio (RR) using the following formula  $RR = (P_1/P_0) = OR / [(1-P_0) + (P_0 \times OR)]$  (75). The log-binomial model will preferentially be used in the absence of convergence or estimability issue for estimating the effect size with RR.

The primary rule for handling the missing data is to consider non-responders all patients who are not confirmed responders.

The primary handling of centers is to ignore in the primary analysis the center effect because 30+ centers should be involved in the study and the number of empty cells in the breakdown of the site by treatment by stratum table can be large (sparse contingency table).

The primary handling of multiplicity of testing will be done through the Hochberg procedure.

The primary handling of heterogeneity of result across strata will be performed through the Breslow-Day test. If the homogeneity hypothesis is rejected, then the estimate of the difference in percentage points between each dose and placebo along with the 95% C.I. will be calculated within each stratum. If the interaction between stratum and treatment (Breslow Day test) is significant it means that the treatment effect has not the same magnitude in diabetic and non-diabetic patients. In the absence of qualitative interaction there will be no further adjustment of the type one error for multiplicity of testing.

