- Main plasma lipids levels (TC, HDL-C, calculated LDL-C, TG and apoA1) change from baseline to end of treatment (week 24) will be compared using GLM with the diabetes and dose as covariates. A mixed model for repeated measures will also be used to compare the time course of the response of each treatment group.
- Adiponectin change from baseline to end of treatment (week 24). Comparison tests and estimates of the difference in the change from baseline will be performed using GLM with the diabetes and dose as covariates. A mixed model for repeated measures will also be used to compare the time course of the response of each treatment group.
- Immunohistochemistry if deemed necessary: change in the semi-quantitative score of ballooning and stellate cell activation from baseline to end of treatment (week 24) will be compared using a Van Elteren rank test stratified on diabetes.

The SAP will provide more details on the presented analyses as well as on other exploratory criteria such as quality of life assessment.

All secondary efficacy analyses will be performed using a mixed model for repeated measures or an ANCOVA model if only one post-randomization measure is available. CMH test stratified on diabetes will be used for qualitative variables.

Exploratory analyses on the biomarkers measurements and other evaluations will be proposed and described in the statistical analysis plan.

The final version of the Statistical Analysis Plan will be issued before freezing of the database the break of the randomization code. Any clarification brought in the SAP concerning handling of data and statistical analyses will prevail over any other interpretations of the protocol unless it is the source of major inconsistencies.

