#### 4.3.6 Per protocol set of patients

This set will be composed of all patients of the FAS free from major protocol deviation, which can bias the estimate of the treatment effect. Patients with major deviations will be listed during the Blind Data Review Meetings and the reason for exclusion will be provided. Post-treatment biopsy evaluable for efficacy not available will be considered as a major protocol deviation.

The figure below summarizes the patient populations to be considered:

Note:

When considering actual treatment received:

- if a patient received both active and placebo IMPs during the study, active IMP will be considered as actual treatment

- if a patient received active IMP at both doses (800 mg and 1200 mg) during the study due to dispensation error(s), the dose of 1200 mg will be considered as actual treatment

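### After a treatment error, the primary FAS analysis leaves the randomised arms although the protocol labels it intent-to-treat, and the SAP's mixed-treatment rule is not listed as a change

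*SAP*

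**What the plan says.** Protocol 9.7.4 (primary efficacy analysis) states: "The primary population will be the intent to treat FAS population composed of all randomized subject who received at least one dose". Protocol 9.5 gives the grouping rule for the same set. After an assignment error, "the actual treatment will be used in the FAS instead of the treatment assigned in the randomization list". SAP 4.3.3 repeats it: "In case of error in the assignment of treatment, the actual treatment will be used in the FAS instead of the treatment assigned". Membership in SAP 4.3.3 is "all randomized patients who received at least one dose of the assigned treatment".

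The SAP defines actual treatment after mixed exposure in a note under the per-protocol set (4.3.6): "if a patient received both active and placebo IMPs during the study, active IMP will be considered as actual treatment". If both doses were dispensed in error, "the dose of 1200 mg will be considered as actual treatment". The note sets no minimum duration of exposure.

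SAP 5.2.2.1 makes the FAS the primary population, and its two p-values settle whether the primary objective is met. The assigned arm is used only in the Randomized set (SAP 4.3.2), where "the treatment assigned in the randomization list will prevail over the actual received treatment". That set is one row of the sensitivity table for the primary endpoint in SAP 5.2.2.2.

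**The concern.** Grouping patients by what they received is an as-treated comparison. Randomisation protects the comparison of assigned arms. Once patients move between arms because of something that happened after randomisation, the deciding test no longer rests on that protection, and the intent-to-treat label is inaccurate.

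Each patient receives five kits over three dispensing visits (protocol 4.3.2 and 4.3.3). Under the SAP 4.3.6 note, one wrong active kit could move a placebo patient into an active arm for the primary test. A reader comparing protocol and SAP would not learn this from SAP 4.6.2, which does list finer points such as the handling of stratification errors.

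For the binary secondary histology endpoints, the sensitivity tables (for example SAP 5.2.3.1) use only the treatment actually received, so no by-arm result would be shown.

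**Working it through.** **1. The texts side by side.**
- Label: intent-to-treat (protocol 9.7.4).
- Grouping after an error: actual treatment (protocol 9.5, SAP 4.3.3).
- Mixed exposure: any active product counts as active, and both doses count as 1200 mg (SAP 4.3.6 note). Protocol 9.5 has no such rule.
- Listed population changes (SAP 4.6.2): screened set, evaluable set, safety set and stratum handling. The mixed-treatment rule is absent.
- Membership: SAP 4.3.3 requires a dose of the assigned treatment, yet its next sentence presupposes that wrongly treated patients are in the set. Protocol 9.7.4 asks only for one dose.

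**2. The plan's own figure.** With n = [p0(1−p0) + p1(1−p1)] × (z₀.₉₈₇₅ + z₀.₈₀)² / (p1−p0)² and (2.2414 + 0.8416)² = 9.505:
- 10% vs 30%: 0.300 × 9.505 / 0.04 = 71.3, so 72 per group.
- 15% vs 35%: 0.355 × 9.505 / 0.04 = 84.4, so 85 per group.

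Both match SAP 4.2. Grouping by assigned arm does not change them.

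**3. A single borderline data set** (assumed counts, pooled z-test). For 19/82 vs 8/82, p = 0.0205.
- Moving one, two or three placebo non-responders to the active arm gives p = 0.0246, 0.0294 or 0.0349.
- Moving one, two or three placebo responders gives p = 0.0076, 0.0025 or 0.0007.

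Starting instead from 25/82 vs 8/82 (p = 0.0009), moving up to three patients leaves p at or below 0.0021.

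**4. How often the verdict changes.** Inputs: 247 randomised (SAP 3.5), 247/3 = 82.3, so 82 per arm; 10% vs 30% from SAP 4.2; 20% on both doses as an assumed weaker effect; k = 1 or 3 placebo patients counted as 1200 mg, also assumed. Every combination of responder counts is enumerated with binomial weights. The test is the unstratified chi-square with the CMH factor (N−1)/N, because stratum sizes are not given. Hochberg rule: both doses are significant if the larger p ≤ 0.05, otherwise one is if the smaller p ≤ 0.025. Verdict: at least one dose better than placebo. The moved patients respond either at the placebo rate or at the 1200 mg rate.

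| Placebo/800/1200 response | k | Moved patients respond at | Power by arm → as treated | Lost / gained | Verdict changed |
|---|---|---|---|---|---|
| 10/30/30 | 1 | placebo rate | 95.3% → 94.8% | 0.79 / 0.31 | 1.1% |
| 10/30/30 | 1 | 1200 mg rate | 94.7% → 95.0% | 0.61 / 0.94 | 1.6% |
| 10/30/30 | 3 | placebo rate | 95.3% → 94.3% | 1.62 / 0.56 | 2.2% |
| 10/30/30 | 3 | 1200 mg rate | 93.4% → 94.9% | 0.76 / 2.27 | 3.0% |
| 10/10/30 | 1 | placebo rate | 85.9% → 84.2% | 2.38 / 0.73 | 3.1% |
| 10/10/30 | 1 | 1200 mg rate | 84.7% → 85.0% | 1.85 / 2.17 | 4.0% |
| 10/10/30 | 3 | placebo rate | 85.9% → 82.7% | 4.50 / 1.32 | 5.8% |
| 10/10/30 | 3 | 1200 mg rate | 82.3% → 85.1% | 2.13 / 4.99 | 7.1% |
| 10/20/20 | 1 | placebo rate | 49.2% → 47.6% | 2.89 / 1.23 | 4.1% |
| 10/20/20 | 1 | 1200 mg rate | 48.1% → 48.0% | 2.57 / 2.47 | 5.0% |
| 10/20/20 | 3 | placebo rate | 49.2% → 46.5% | 5.40 / 2.65 | 8.1% |
| 10/20/20 | 3 | 1200 mg rate | 45.8% → 47.7% | 3.79 / 5.69 | 9.5% |

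One 800 mg patient counted as 1200 mg and responding at the 800 mg rate changes the verdict in 0.6%, 1.4% and 1.9% of trials in the three scenarios.

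**5. Type I error.** Two-sided family-wise error with k = 0, 1, 3 is 4.31%, 4.69%, 4.64% at a common response of 10%, and 4.89%, 4.67%, 4.66% at 20%. All stay below 5%.

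**The case against.** The strongest reply is that the rule is the protocol's own, fixed in advance and backed by a by-arm check. Most of that stands. Protocol 9.5 already groups the FAS by actual treatment, so a reader who infers that the SAP overturned an intent-to-treat protocol would be wrong; the conflict lies within the protocol. A reader might also infer that the by-arm analysis is missing. It is not: protocol 9.7.4 and SAP 5.2.2.2 plan it for the primary endpoint, with the same non-responder imputation as the primary analysis. The secondary endpoints, where it is absent, do not decide the primary objective. The mixed-treatment note does give content to a term that protocol 9.5 leaves undefined, and leaving it out of SAP 4.6.2 is a matter of record-keeping.

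Two further inferences fail. One is that the rule costs power, or that it favours the drug. The table shows a net loss if moved patients respond at the placebo rate. At the 1200 mg rate it shows almost no net change with one patient and a net gain with three. Exposure after an error may be partial, so the direction is unknown. The other is that errors occurred: the SAP provides for them but gives no count.

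What remains is that specifying an as-treated grouping in advance does not make it intent-to-treat, and a sensitivity row does not put the deciding test back on the randomised arms.

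**Conclusion.** The point holds as a minor one. The intent-to-treat label and the as-treated grouping cannot both describe the primary analysis, and the mixed-treatment rule is undeclared as a change. If errors occur, the deciding analysis departs from the randomised comparison.

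For one to three placebo patients counted as 1200 mg, the verdict changes in about 1% to 9% of trials (1.1% to 9.5% in the table). With no errors the treatment grouping is unchanged. No power loss, power gain or material type I error inflation should be claimed.

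These figures rest on assumed error counts, equal arms of 82, an unstratified test and two assumed response rates for the moved patients. The SAP was written against protocol 5.1 and the protocol available here is 5.0, so the comparison with protocol 9.5 assumes that section did not change.

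**What to change.** - In SAP 4.3.3, state that all FAS efficacy analyses use the treatment assigned in the randomisation list. Define membership as randomised patients who received at least one dose of any study treatment, in line with protocol 9.7.4.
- List this in SAP 4.6.2 as an explicit change from protocol 9.5. Protocol 9.7.4 does say "Any clarification brought in the SAP concerning handling of data and statistical analyses will prevail over any other interpretations of the protocol", but the same sentence makes an exception where the clarification causes major inconsistencies, and replacing an explicit grouping rule goes beyond interpreting it. If the sponsor considers the change more than a clarification, a protocol amendment is needed.
- Keep actual treatment and the mixed-treatment rule for the Safety set and, if wanted, for one as-treated sensitivity analysis of the primary endpoint. List the rule in SAP 4.6.2.

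The cost is wording in SAP 4.3.3 and 4.3.6, entries in 4.6.2, efficacy outputs regrouped by assigned arm, and possibly the amendment. Sample size is unchanged.

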#### 4.3.4 Safety set of patients

The safety set of patients will consist of the FAS who will have taken at least one dose of treatment, regardless any protocol deviations. ‘No adverse event’ confirmed by the investigator in the AE form will be considered as a post-baseline assessment of safety.

In case of treatment error, the actual treatment will be used.

#### 4.3.5 Evaluable patient population (EPP)

The evaluable patient population will consist of the FAS after exclusion of all patients without post-randomization efficacy assessment (SAF score at visit 3).

- All patients who prematurely discontinued the study treatment:
  - o due to a reason linked to study treatment intake (adverse event) or lack of efficacy (recorded in ‘Other’) will be included in the EPP. In this case, the patient will be non-responder (see ‘Secondary imputation method’ in section 4.1.6.3).
  - o for a reason not linked to study treatment intake (such as lost to follow-up or consent withdrawal) will be excluded from the EPP.

The reasons of study treatment premature discontinuation will be solely reviewed during BDRM to correctly define the EPP.

[figure not shown]
- Patients that completed their study treatment up to Visit 3:
  - o with an efficacy assessment at Visit 3 (biopsy performed, readable and performed within 14 days following last intake) will be included in the EPP.
  - o without efficacy assessment at Visit 3 (biopsy not performed because patient refusal, biopsy not readable, biopsy not performed within 14 days following last intake...) will be excluded from the EPP.

The same rule will be applied for other binary efficacy variables.

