#### **- Set of evaluable patients**

The set of evaluable patients will consist of the FAS after exclusion of all patients without post-randomization assessments. Concerning the primary endpoint, the absence of post randomization assessment will be considered a failure and the patient will therefore be evaluable if the withdrawal is possibly due to lack of efficacy or safety concern. The same rule will be applied for other binary efficacy variables.

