##### 2. Secondary imputation method

Patients with a missing data will be considered as Non-responder in case of premature treatment withdrawals due to: Adverse event or Other: Lack of efficacy. The other reasons will be clearly reviewed during Blind Data Review Meeting (BDRM) to identify 'Lack of efficacy'. In all other cases, missing data will remain missing.

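### The Evaluable population (SAP 4.3.5) excludes some early discontinuers by their reason for stopping even when a readable Visit 3 biopsy exists, contradicting its own first sentence and the protocol

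*SAP*

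**What the plan says.** SAP 4.3.5 defines the Evaluable patient population (EPP) in two layers.

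- The lead sentence concerns whether an assessment exists: "The evaluable patient population will consist of the FAS after exclusion of all patients without post-randomization efficacy assessment (SAF score at visit 3").
- The bullets then divide the FAS by treatment completion. Completers are sorted by whether a readable, timely Visit 3 biopsy exists. The other branch covers "All patients who prematurely discontinued the study treatment" and sorts only by reason. Those who stopped for an adverse event or lack of efficacy are included: "In this case, the patient will be non-responder", with a cross-reference to the Secondary imputation method. Those who stopped "for a reason not linked to study treatment intake (such as lost to follow-up or consent withdrawal) will be excluded from the EPP".

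Other places bear on the same patients.

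- Protocol 9.5: "The set of evaluable patients will consist of the FAS after exclusion of all patients without post-randomization assessments". The reason for withdrawal matters there only once the assessment is absent.
- SAP 4.1.6.3, Secondary imputation method: "Patients with a missing data will be considered as Non-responder in case of premature treatment withdrawals" for an adverse event or lack of efficacy. It acts on missing data only.
- SAP 4.1.6.3, Note, on all biopsy-based analyses: "data collected at actual V3 should be taken into account as well as data collected at Visit 3 being an early treatment discontinuation".
- SAP 4.5.4.1.3 treats a Week 24 biopsy as available whenever SAF-A is non-missing at Visit 3, without requiring completion of treatment.
- SAP 4.6.2 presents the EPP text as added detail and discloses no new exclusion.

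**The concern.** A sensitivity analysis on evaluable patients is meant to show what happens when outcomes that were never observed are handled differently. As worded, the rule can also remove outcomes that were observed, and removal depends on why the patient stopped. That reason arises after randomisation and may be distributed differently across arms.

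The EPP with secondary imputation is one of five sensitivity analyses of the primary endpoint (SAP 5.2.2.2). It is also a sensitivity analysis of four secondary endpoints: NASH improvement, resolution of NASH without worsening of fibrosis, fibrosis improvement without worsening of NASH, and resolution of NASH with fibrosis improvement (SAP 5.2.3.1 to 5.2.3.4). A programmer working from the lead sentence and one working from the bullets could build different populations from the same page.

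**Working it through.** No figure in the plan depends on this rule, so the main check compares the texts. An illustration of size follows.

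**Step 1. A FAS patient who stops for an unrelated reason and has a readable Visit 3 SAF score**

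- SAP 4.3.5, lead sentence: in the EPP.
- SAP 4.3.5, discontinuer bullet: out.
- Protocol 9.5: in, because a post-randomisation assessment exists.
- SAP 4.1.6.3, Note: the biopsy counts.
- SAP 4.5.4.1.3: the biopsy is available.

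Only the bullet removes the patient. This contradiction is direct.

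**Step 2. A FAS patient who stops for an adverse event or lack of efficacy and has a readable Visit 3 SAF score**

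- SAP 4.3.5, lead sentence and bullet: in the EPP, so membership is not in conflict.
- SAP 4.3.5, bullet read alone: non-responder.
- Secondary imputation method, which the bullet cites: nothing is missing, so the observed result stands.
- Protocol 9.5: the failure rule applies only where the assessment is absent, so the observed result stands.

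The bullet and the method it cites need to be aligned.

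**Step 3. Can such patients exist?** Protocol 5.3.4 asks early withdrawals to have the Visit 3 procedures if possible, and protocol 5.3.5 places the biopsy at that visit. SAP 5.1.1 splits Visit 3 into early-termination and week-24 visits. Its discontinuation reasons include sponsor request, forbidden concomitant treatment, a problem with the study product and personal reasons. None of these rules out a biopsy.

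**Step 4. Size of one patient's effect.** Inputs: 247 randomised (SAP 3.5), so 247/3 is about 82 per arm; active-arm rate 10% + 20 points = 30% (SAP 4.2), i.e. 24.6 responders of 82.

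- Drop an observed responder: 23.6/81 = 29.1%, about -0.9 points.
- Drop an observed non-responder: 24.6/81 = 30.4%, about +0.4 points.
- Recode an observed responder as a non-responder: 23.6/82 = 28.8%, about -1.2 points.
- Recode an observed non-responder: no change.

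**Step 5. Several patients dropped (the firm part).** Assume 75 per arm, all with a biopsy, so 22.5 responders at 30%, and let b unrelated-reason stoppers have a readable biopsy. If they respond at their arm's rate, dropping b = 2, 4 or 8 leaves the rate at 30.0% and reduces n to 73, 71 or 67. If they do not, the bounds for b = 4 are (22.5 - 4)/71 = 26.1% when all four responded and 22.5/71 = 31.7% when none did.

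**Step 6. If the adverse-event bullet were also applied literally.** Let a patients stop for an adverse event or lack of efficacy with a readable biopsy, all stoppers responding at their arm's rate. The rate is (75 - a - b) × p/(75 - b).

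| a = b per arm | n | Placebo (p = 10%) | Active (p = 30%) | Difference if a occurs in the active arm only |
|---|---|---|---|---|
| 0 | 75 | 10.0% | 30.0% | 20.0 points |
| 2 | 73 | 9.7% | 29.2% | 19.2 points |
| 4 | 71 | 9.4% | 28.3% | 18.3 points |
| 8 | 67 | 8.8% | 26.4% | 16.4 points |

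In the last column b is removed from both arms and placebo stays at 10.0%. The counts a and b are assumptions; the documents give none.

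**The case against.** The best defence is that a qualifier was simply left out. The lead sentence and protocol 9.5 share a structure: set aside patients with no assessment, then bring some back by reason for withdrawal. The examples in the bullet, loss to follow-up and consent withdrawal, typically describe patients with no final biopsy. On that reading no observed outcome is lost. This is plausible as intent, but it is not what the bullet says, and Step 3 shows other reasons compatible with a biopsy.

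The populations figure announced in SAP 4.3.6 is not visible in the text available here and may settle the matter. The written definition would still have to agree with it. Protocol 9.7.4 lets SAP clarifications prevail unless they cause major inconsistencies, but that cannot resolve a conflict within the SAP.

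A reader might infer that the SAP overwrites observed responses of patients who stopped for an adverse event or lack of efficacy. The documents do not establish this: the sentence points to the Secondary imputation method, which is confined to missing data. A reader might also count every affected patient as 1.2 percentage points. That holds only for an observed responder recoded as a non-responder (Step 4).

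It also stands that reasons for stopping are reviewed at the blind data review. This limits knowing manipulation, although it does not restore a discarded outcome.

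**Conclusion.** The contradiction is real and confined to the EPP. The unrelated-reason bullet excludes patients whom the lead sentence, protocol 9.5 and the SAP's biopsy rules would keep. The wording for adverse events and lack of efficacy is an ambiguity between two SAP sections.

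Nothing here supports an inference that the primary result is at risk. The primary analysis uses the FAS with missing data as non-response, and both it and the FAS observed-cases analysis keep early-discontinuation biopsies.

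The size cannot be derived, because the number of discontinuers with a readable Visit 3 biopsy is not given. If there are none, there is no effect. If there are a few, dropping them shifts an arm's rate only to the extent that they respond differently from the rest of the arm. The table in Step 6 shows what the literal reading of both bullets would do under assumed counts. The point deserves correction because the analysis is meant to support robustness and the repair costs almost nothing.

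**What to change.** Amend SAP 4.3.5 as follows.

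- Limit both reason-based bullets to premature discontinuers without a readable Visit 3 SAF score.
- State that any discontinuer with a readable Visit 3 SAF score is in the EPP with the observed result, whatever the reason for stopping.
- Keep the Secondary imputation method in 4.1.6.3 as applying to missing data only, and check that the populations figure agrees.

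If a biopsy time window is kept, apply it without regard to the reason for stopping. First reconcile the 14-day and 8-day limits that both appear under observed cases under treatment in 4.1.6.3. A window combined with the reason rules would otherwise bring back the same problem for late but readable biopsies.

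The cost is SAP wording and a matching derivation, best done before database lock. No new data are needed, and the sample size and primary analysis do not change.
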